9.0 STUDY MONITORING

Nu-Life will monitor the study according to good clinical practice. Monitoring will begin upon enrollment of the first 5 patients at the site and will continue every 8 weeks until completion of the study. The Principal Investigator will work with a representative from Nu-Life to ensure the study is conducted according to this protocol and that all study matters are properly communicated.

Appendix 1: Study Process Maps

Figure 1- Baseline Visit

[figure not shown]
[figure not shown]
[figure not shown]

Figure 2- Weekly Visits

On-Treatment Weeks

Off-Treatment Weeks

miro

Appendix 2: Eligibility Checklist

Nu-V3 RCT PROTOCOL

SCREENING AND ELIGIBILITY CHECKLIST

A Randomized, Phase II, Open-Label Study Evaluating the Nu-V3 Cranial Nerve Stimulation Treatment Device in Patients with Chronic Pain, Anxiety, Depression, and/or Sleeplessness

Subject Initials:
Subject Identification Number:
Date of Consent:

STATEMENT OF ELIGIBILITY:

This subject is eligible / ineligible for participation in the study.

Investigator Signature: _____ Date: _____

Printed Name: _____

INCLUSION CRITERIA (all questions should be answered YES – If question is answered No, subject is not eligible for participation)

Yes	No	
		Participant is at least 18 years of age
		Participant presents with one or more of the following symptoms: chronic pain, anxiety, depression, and/or sleeplessness
		Participant must score greater than or equal to a 5/10 for their primary symptom on the Baseline Symptom Questionnaire
		Study cohort must have an available accrual slot for the participant respective of their primary symptom
		Participant has signed the Informed Consent Form

If any of the above boxes are checked "No", the subject does not meet eligibility criteria

EXCLUSION CRITERIA (all questions should be answered No – If question is answered Yes, subject is not eligible for participation)

Yes	No	
		Participants with a hearing aid
		Participants with a pacemaker
		Participants with an irregular heart rate or a heart rate lower than 60 beats per minute (bradycardia)
		Have had a transplant within the last 2 years
		Have had a heart attack or cardiac bypass surgery within the last 12 months
		Patients with complaints of dizziness or lightheadedness within the last 3 months
		Women who are pregnant
		Participants with Diabetic Retinopathy
		Current Ear infection
		SBP < 100 and/or DBP < 60
		History of uncontrolled bipolar disorder within the last 12 months
		History of uncontrolled seizures within the last 12 months
		History of aneurysms
		History of syncope within the last 12 months
		Participants who have had a TIA or stroke within the last 12 months
		Participants with health problems deemed at risk for the study by the Principal Investigator
		Participants with any changes to Pain/Anxiety/Depression/Sleeplessness medications within last 60 days (participants that do not meet this medication change washout period may be delayed until 60-day period is met)
		Participants that are currently under adjudication process for disability support, VA or other

If any of the above boxes are checked "Yes", the subject does not meet eligibility criteria

Appendix 3: IRB Unanticipated Problem Form

Nu-V3 Unanticipated Problem Form

Nu-V3 Version 1.0 Version Date: 07/Nov/2017	 Initial Report: _____ dd / mmm / yyyy	 Follow-up No. _____ _____ dd / mmm / yyyy	 Follow-up No. _____ _____ dd / mmm / yyyy	
Investigator Name: _____		Site: _____		
DEMOGRAPHICS				
Gender  Female  Male	Date of Birth _____/_____/_____ dd / mmm / yyyy	Height _____  in  cm	Weight _____  lbs  kg	
ADVERSE EVENT INFORMATION				
SAE Term (diagnosis preferred over signs/symptoms):				
Onset Date _____/_____/_____ dd / mmm / yyyy	Serious Criteria (select all that apply)  Requires/prolongs inpatient hospitalization*  Life-threatening  Persistent or significant disability/incapacity  Congenital Anomaly/Birth Defect  Important medical event  Death ^b	CTCAE Grade  Grade 1 - Mild  Grade 2 - Moderate  Grade 3 - Severe  Grade 4 - Life-threatening  Grade 5 - Fatal	Outcome  Ongoing  Resolved  Resolved w/ sequelae ^c  Fatal	
Stop Date _____/_____/_____ DD / MON / YYYY	Hospitalization: Date of Admission _____ dd / mmm / yyyy		Date of Discharge _____ dd / mmm / yyyy	
Death:				
Date of death _____ dd / mmm / yyyy		Was autopsy completed?  Yes  No If yes, please forward report.		
		Is death certificate available?  Yes  No If yes, please forward.		
Describe sequelae:				
STUDY DEVICE INFORMATION				
Study Device Nu-V3  N/A	Date of First Use _____/_____/_____ dd / mmm / yyyy	Date of Last Use before SAE Onset _____/_____/_____ dd / mmm / yyyy	Relationship to Device  Related  Unrelated	Action taken with Device  None  Dose Reduced  Interrupted  Discontinued
Serial# _____	Possible Cause of SAE other than Study Device (select all that apply):  Concurrent condition  Concurrent medication  Other, specify: _____ _____ Condition term Medication name			

Effective Date: 07NOV2017
Page 1 of 2

Document Title: Nu-V3 Unanticipated Problem Form

Nu-V3 Version 1.0 Version Date: 07/Nov/2017		Site Name:		Subject #:		
Nu-V3 Treatment Modifications: If action taken = interrupted or discontinued, did event stop once device was stopped?  Yes  No If action taken = interrupted, did event recur once device was restarted?  Yes  No						
RELEVANT LABORATORY/DIAGNOSTIC TESTS  None						
Test Name		Date <small>dd/mm/yy</small>	Results/Value	Unit	Normal Range	
RELEVANT CONCOMITANT MEDICATIONS  None						
Medication	Start Date <small>dd/mm/yy</small>	Stop Date or Ongoing <small>dd/mm/yy</small>	Dose & Unit	Frequency	Route	Indication
		or  Ongoing				
		or  Ongoing				
		or  Ongoing				
		or  Ongoing				
RELEVANT MEDICAL HISTORY  None						
Diagnosis		Start Date <small>dd/mm/yy</small>	Stop Date or Ongoing <small>dd/mm/yy</small>			
			or  Ongoing			
			or  Ongoing			
			or  Ongoing			
			or  Ongoing			
NARRATIVE SUMMARY Describe the event in detail from onset through resolution. Include rationale for causality and any interventions given.						
REPORTER INFORMATION						
Investigator Name:		Phone:		Email address:		
Reporter Name:		Phone:		Email address:		
INVESTIGATOR SIGNATURE VERIFIES THAT EVENT HAS BEEN REVIEWED AND INVESTIGATOR CONCURS WITH THIS REPORT. I, the undersigned investigator, attest that I have reviewed this SAE Report. NOTE: Sign and date.						
Signature:			Date:			
Signature:			Date:			
Signature:			Date:			

SAE report may be emailed to Nu-Life Solutions Executive Medical Team
 Email: [contact]

Appendix 4: Adverse Event Form

Subject ID _____ Date (dd/mmm/yyyy): ____/____/____

Adverse Events Form

1. Has the participant experienced any adverse events?

- No (end of form)
 Yes (update log below)

2. Adverse Event Log (CTCAE 5.0)

Grade 1=Mild Grade 2=Moderate Grade 3=Severe Grade 4=Life-threatening Grade 5=Death
 Attribution Grading: A=unrelated B=unlikely C=possibly D=probably E=definitely

Event Name	SAE?	Grade	Attribution	Start Date (dd/mmm/yyyy)	End Date (dd/mmm/yyyy)	Treatment held or withdrawn?
	y/n		A B C D E			
	y/n		A B C D E			
	y/n		A B C D E			
	y/n		A B C D E			
	y/n		A B C D E			
	y/n		A B C D E			
	y/n		A B C D E			
	y/n		A B C D E			
	y/n		A B C D E			
	y/n		A B C D E			
	y/n		A B C D E			
	y/n		A B C D E			
	y/n		A B C D E			
	y/n		A B C D E			
	y/n		A B C D E			
	y/n		A B C D E			
	y/n		A B C D E			
	y/n		A B C D E			
	y/n		A B C D E			
	y/n		A B C D E			

Appendix 5: Medical History Form

Subject ID _____ Date (dd/mmm/yyyy): ____/____/____

Medical History Form

Please answer the following questions about your past and current medical history.

1. Do you have a history of any significant medical problems or chronic disease requiring a physician's care?

Yes (If Yes, please list below) No

Medical Problem	Date of Diagnosis (dd/mmm/yyyy)	Are you having trouble with this problem now?
	/ /	 Yes  No
	/ /	 Yes  No
	/ /	 Yes  No
	/ /	 Yes  No
	/ /	 Yes  No
	/ /	 Yes  No
	/ /	 Yes  No
	/ /	 Yes  No
	/ /	 Yes  No
	/ /	 Yes  No

2. Have you had trouble with or sought medical attention for (please include even if stated in Question 1).

Irregular Heart Rate	 Yes  No	
Cardiac Arrhythmia	 Yes  No	
Heart Disease	 Yes  No	

Subject ID _____ Date (dd/mmm/yyyy): ____/____/____

Chest Pain	 Yes  No	
Heart Attack	 Yes  No	
Heart Murmur	 Yes  No	
Dizziness/ Lightheadedness	 Yes  No	
Diabetic Retinopathy	 Yes  No	
Bradycardia	 Yes  No	
Epilepsy, Seizures, or Convulsions	 Yes  No	
Aneurysms	 Yes  No	
Syncope	 Yes  No	
TIA or Stroke	 Yes  No	
Drugs or Alcohol	 Yes  No	

3. Have you had trouble with or sought medical attention for (please include even if stated in Question 1).

High Blood Pressure	 Yes  No	
Head Injury	 Yes  No	
Chronic Neck or Back Pain	 Yes  No	
Hypothyroidism	 Yes  No	 Stable  Unstable
Hyperthyroidism	 Yes  No	 Stable  Unstable
Rheumatoid Arthritis	 Yes  No	
Inflammatory Arthritis	 Yes  No	
Psoriatic Arthritis	 Yes  No	

Subject ID _____ Date (dd/mmm/yyyy): ____/____/____

Irritable Bowel Syndrome	 Yes  No	
Neuropathy	 Yes  No	 Motor  Sensory
Headaches	 Yes  No	 Tension  Migraine

4. **FEMALES ONLY**; if male, skip to Question #5.
- a. Are you pregnant, or trying to become pregnant? Yes No
 - b. Are you using birth control? Yes No
 - c. If 'Yes', describe:
5. Have you had any surgery in the past three months? Yes No
If 'Yes', describe:
6. Have you ever been hospitalized for psychiatric reasons? Yes No
7. Have you ever been diagnosed with any of the following disorders?

Depression	 Yes  No	 Less than 3 months ago  3-12 months ago  Greater than 1 year ago
Bipolar Disorder	 Yes  No	 Less than 3 months ago  3-12 months ago  Greater than 1 year ago
Panic Disorder	 Yes  No	 Less than 3 months ago  3-12 months ago  Greater than 1 year ago
Phobia	 Yes  No	 Less than 3 months ago  3-12 months ago  Greater than 1 year ago

Subject ID _____ Date (dd/mmm/yyyy): ____/____/____

PTSD	 Yes  No	 Less than 3 months ago  3-12 months ago  Greater than 1 year ago
Obsessive Compulsive Disorder	 Yes  No	 Less than 3 months ago  3-12 months ago  Greater than 1 year ago
General Anxiety Disorder	 Yes  No	 Less than 3 months ago  3-12 months ago  Greater than 1 year ago
Schizophrenia	 Yes  No	 Less than 3 months ago  3-12 months ago  Greater than 1 year ago
Schizo-Affective Disorder	 Yes  No	 Less than 3 months ago  3-12 months ago  Greater than 1 year ago

9. Have you ever been given any medications for emotional problems, such as anti-depressant, anti-anxiety or anti-psychotic medications? Yes No

Appendix 6: Treatment Form

Weekly Treatment Form

Subject ID _____ Date (dd/mmm/yyyy): ____/____/____

1. Device Serial Number: _____

2. Was the device placed on the participant's left ear?

Yes No If no, reason why: _____

Appendix 7: Medications and Standard of Care Treatment Form

Subject ID _____	Date (DD/MMM/YYYY): ____/____/____
------------------	------------------------------------

Medications and Standard of Care Treatment Form

Please record all medications and other standard of care treatments related to any of the study indications, chronic pain, anxiety, depression, or sleeplessness. Include any treatments, supplements, and alternative holistic therapies.

1. Have the participant's medications changed?

No (continue to other treatments section)
 Yes (update the medications log below)

2. Medications Log – *Include any medications, herbal/non-herbal supplements, or medical marijuana used in the treatment of symptoms for chronic pain, anxiety, depression, or sleeplessness.*

Med Name	Dose	Unit	Frequency	Start Date (dd/mmm/yyyy)	End Date (dd/mmm/yyyy)	Indication

Nu-Life Solutions
Version Date: December 30, 2021

3. Treatment Log - *Include any treatments related to symptom relief for chronic pain, anxiety, sleeplessness, or depression.*

Examples include but are not limited to:

- Aromatherapy
- Acupuncture
- Cryotherapy
- Meditation
- Tai Chi

Therapy Name	Start Date (dd/mmm/yyyy)	End Date (dd/mmm/yyyy)	Indication

Appendix 8: ePRO Questionnaires

DATE: _____
Week # _____

Device/Pad serial # _____
Subject ID _____

Complete Patient ePRO Questionnaire Packet

Form DQ-7: Patient Demographics

Subject ID

Date (dd/mmm/yyyy):

___/___/___

Age

What is your age? _____

Sex at Birth

- Male
 Female
 Other
 Choose not to answer

Marital Status

- Single
 Married
 Divorced
 Widowed

Primary Language?

Self-Description (please choose one):

- Arabic
 Bengali
 English
 French
 German
 Hindi/Urdu
 Japanese
 Mandarin
 Portuguese
 Punjabi
 Russian
 Spanish
 Other

Race/Ethnicity

Self-Description (please choose one):

- American Indian
 Asian-American/Oriental/Pacific Islander
 Asian East Indian
 Black/African-American
 Mexican-America/Chicano
 Puerto-Rican
 Other Hispanic
 White/Caucasian
 Other

Education History

What is the highest degree or level of school you have completed? *If currently enrolled, highest degree received.*

- No schooling completed
 Nursery school to 8th grade
 Some high school, no diploma
 High school graduate, diploma or GED
 Some college credit, no degree
 Trade/technical/vocational training
 Associate degree
 Bachelor's degree
 Master's degree
 Professional degree
 Doctorate degree

Service Status

Are you now, or have you ever served as a member of the armed forces?

- Yes, I am a military veteran
 Yes, I am an active duty member
 No, I have never served in the armed forces

Are you a First Responder (firefighter, EMS, law enforcement, etc)?

- Yes, I am current or former First Responder
 No, I have never been a First Responder

PEG: A Three-Item Scale Assessing Pain Intensity and Interference

Subject ID: _____ Date (dd/mmm/yyyy): ____/____/____

PEG: A Three-Item Scale Assessing Pain Intensity and Interference

1. What number best describes your pain on average in the past week?

0 1 2 3 4 5 6 7 8 9 10
No pain _____ Pain as bad as
you can imagine

2. What number best describes how, during the past week, pain has interfered with your enjoyment of life?

0 1 2 3 4 5 6 7 8 9 10
No pain _____ Pain as bad as
you can imagine

3. What number best describes how, during the past week, pain has interfered with your general activity?

0 1 2 3 4 5 6 7 8 9 10
No pain _____ Pain as bad as
you can imagine

From Krebs et al., 2009.

GAD-7 - Generalized Anxiety Disorder 7-item Scale

Subject ID: _____

Date (dd/mmm/yyyy): ____/____/____

Over the last 2 weeks, how often have you been bothered by the following problems?	Not at all sure	Several days	Over half the days	Nearly every day
1. Feeling nervous, anxious, or on edge	0	1	2	3
2. Not being able to stop or control worrying	0	1	2	3
3. Worrying too much about different things	0	1	2	3
4. Trouble relaxing	0	1	2	3
5. Being so restless that it's hard to sit still	0	1	2	3
6. Becoming easily annoyed or irritable	0	1	2	3
7. Feeling afraid as if something awful might happen	0	1	2	3
Add the score for each column	+	+	+	
Total Score (add your column scores) =				

If you checked off any problems, how difficult have these made it for you to do your work, take care of things at home, or get along with other people?

- Not difficult at all _____
- Somewhat difficult _____
- Very difficult _____
- Extremely difficult _____

Source: Spitzer RL, Kroenke K, Williams JBW, Lowe B. A brief measure for assessing generalized anxiety disorder. *Arch Intern Med.* 2006;166:1092-1097.

PHQ-9- Patient Health Questionnaire

Subject ID: _____ Date (dd/mmm/yyyy): ____/____/____

Over the last 2 weeks, how often have you been bothered by any of the following problems?
(use "✓" to indicate your answer)

	Not at all	Several days	More than half the days	Nearly every day
1. Little interest or pleasure in doing things	0	1	2	3
2. Feeling down, depressed, or hopeless	0	1	2	3
3. Trouble falling or staying asleep, or sleeping too much	0	1	2	3
4. Feeling tired or having little energy	0	1	2	3
5. Poor appetite or overeating	0	1	2	3
6. Feeling bad about yourself—or that you are a failure or have let yourself or your family down	0	1	2	3
7. Trouble concentrating on things, such as reading the newspaper or watching television	0	1	2	3
8. Moving or speaking so slowly that other people could have noticed. Or the opposite – being so fidgety or restless that you have been moving around a lot more than usual	0	1	2	3
9. Thoughts that you would be better off dead, or of hurting yourself	0	1	2	3

add columns + +

(Healthcare professional: For interpretation of TOTAL, TOTAL: please refer to accompanying scoring card).

10. If you checked off any problems, how difficult have these problems made it for you to do your work, take care of things at home, or get along with other people?	Not difficult at all	_____
	Somewhat difficult	_____
	Very difficult	_____
	Extremely difficult	_____

PROMIS Item Bank v1.0 - Sleep Disturbance - Short Form 4a

Subject ID: _____

Date (dd/mmm/yyyy): ____/____/____

In the past 7 days...

		Very poor	Poor	Fair	Good	Very good
1	My sleep quality was					

In the past 7 days...

		Not at all	A little bit	Somewhat	Quite a bit	Very much
2	My sleep was refreshing.					
3	I had a problem with my sleep.....					
4	I had difficulty falling asleep					

PATIENTS' GLOBAL IMPRESSION OF CHANGE (PGIC) SCALE

Subject ID: _____

Date (dd/mmm/yyyy): ____/____/____

Chief Complaint (Presenting Problem): _____

Since beginning treatment at this clinic, how would you describe the change (if any) in ACTIVITY LIMITATIONS, SYMPTOMS, EMOTIONS, and OVERALL QUALITY OF LIFE, related to your painful condition? Please circle the number below, that matches your degree of change since beginning care at this clinic for the above stated chief complaint.

No change	Almost the same	A little better	Somewhat better	Moderately better	Better	A great deal better
1	2	3	4	5	6	7

Explanation:

- | | |
|--|--|
| 
 1 = No change (or condition has got worse) 2 = Almost the same, hardly any change at all 3 = A little better, but no noticeable change 4 = Somewhat better, but the change has not made any real difference | 
 5 = Moderately better, and a slight but noticeable change 6 = Better, and a definite improvement that has made a real and worthwhile difference 7 = A great deal better, and a considerable improvement that has made all the difference |
|--|--|

Patient's signature: _____

NOTE TO HEALTH CARE PROVIDER

A significant, favorable change is a score of 5-7.
 No significant change is a 1-4 response.
 Note, this a dichotomous scale (5-7 = yes; 1-4 = no).
 A 2-point change is significant from their last reported score.

[figure not shown]
Reference: Hurst H, Bolton J. Assessing the clinical significance of change scores recorded on subjective outcome measures. Journal of Manipulative Physiological Therapeutics (JMPT) 2004;27:26-35.

Subject ID _____ Date (DD/MMM/YYYY): ____/____/____

[figure not shown]

Form PTB-6: Patient's Perceived Treatment Benefit

1. On a scale of 0-10, how much benefit do you feel you have received from the Nu-V3 treatment in helping your symptoms?

[figure not shown]
2. On a scale of 0-10, how much has your daily activity level improved?

3. Do you feel that your as needed medications have decreased from using the device?

Yes
 No

4. How comfortable was the Nu-V3 Device to wear?

5. Have you had any major discomfort from the device?

Yes; please continue to question 6
 No

6. If yes to question 5, did adjusting the device correct the discomfort?

Yes
 No

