8.0 STUDY ENDPOINT and DATA ANALYSIS

8.1 Primary Endpoints: Primary endpoints consisted of the following:

Safety: At screening/baseline, a medical history will be obtained to capture relevant underlying conditions. The screening/baseline examinations will include BP, and HR. Baseline signs and symptoms are those that are assessed within 14 days prior to week 1 treatment.

Concomitant medications will be collected from within 14 days prior to enrollment through the study treatment period and maintenance period (see Study Assessments Table section 4.1).

The primary safety endpoint is the occurrence of reported unanticipated problems involving risk to subjects or others (“UPIRTSOs”). These UPIRTSOs are defined as those problems which alter the risks to subjects or others. This includes any study suspensions or holds. The primary safety endpoint analyses will be based on a risk-benefit conclusion.

Effectiveness: There are four instruments measuring participant’s symptoms of chronic pain, anxiety, depression, and sleeplessness. The primary effectiveness endpoint is a statistically significant reduction in one or more of measures of: chronic pain, anxiety, depression, or sleeplessness between baseline and 12 or 24 weeks after initiating treatment.

The null hypothesis to disprove is that there is no statistically significant reduction from baseline to 12 or 24 weeks in mean chronic pain, anxiety,

depression, or sleeplessness symptom severity scores using the Nu-V3 device compared with the usual care cohort.

The instruments used in this study are:

Chronic Pain – Pain intensity (P), interference with enjoyment of life (E), and interference with general activity (G) (PEG Scale),

The PEG is a three-item instrument that measures pain intensity (one item) and pain interference (two items). Each item is valued from 0 (no pain/interference) to 10 (as bad as you can imagine). The instrument score is calculated as the average of the three item values.

Anxiety - Generalized Anxiety Disorder 7-item (GAD-7)

The GAD-7 is a seven-item instrument that measures respondents' symptoms of anxiety. Each item is scored on a four-point Likert scale, and values range from 0 ("Not at all") to 3 ("Nearly every day".) Items are summed to determine the instrument's score. Values of 10 or higher have been associated with moderate anxiety, while values of 15 or higher have been associated with severe anxiety.

Depression - Patient Health Questionnaire (PHQ-9)

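### PEG items 2 and 3 ask about interference but carry the pain-intensity labels of item 1, which conflicts with section 8.1 and blurs what two thirds of the pain score measures

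*Protocol*

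**What the plan says.** Protocol section 8.1 defines the instrument: "The PEG is a three-item instrument that measures pain intensity (one item) and pain interference (two items". It gives one description of the response scale for all items, "Each item is valued from 0 (no pain/interference) to 10 (as bad as you can imagine", and one scoring rule: "The instrument score is calculated as the average of the three item values". The PEG is the chronic pain instrument among the four that define primary effectiveness: "The primary effectiveness endpoint is a statistically significant reduction in one or more of measures of: chronic pain, anxiety, depression, or sleeplessness".

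The PEG form is in Appendix 8. Item 1 asks about average pain. Item 2 reads "What number best describes how, during the past week, pain has interfered with your enjoyment of life" and item 3 reads "What number best describes how, during the past week, pain has interfered with your general activity". The response line under each of the three items is the same and begins "No pain _____ Pain as bad as"; it closes by completing the worst-imaginable-pain label. No label on the PEG form mentions interference.

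**The concern.** The question and the response scale of items 2 and 3 refer to different things. The slash in section 8.1's zero label makes sense only if zero means no pain on the intensity item and no interference on the other two. The form does not make that distinction. A patient who still has pain but whose activity has recovered has no clearly correct low answer on item 3, because a zero would also state that there is no pain.

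At stake is what the pain score represents. If some patients answer items 2 and 3 by the labels, a change in interference is diluted and a change in intensity is counted more than once. The score feeds the primary endpoint, and also two secondary endpoints in section 8.2: time to a 30% reduction in any domain, and percentage change on each instrument. Participants in both arms complete the PEG whatever their primary symptom. An analysis plan cannot repair this afterwards, because the recorded number does not show which question the patient answered.

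**Working it through.** **Inputs from the protocol**
- Construct split: 1 intensity item, 2 interference items (section 8.1).
- Score: unweighted mean of three items (section 8.1), so each item has weight 1/3.
- Labels: intensity labels under all three items (Appendix 8).

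**Inputs not in the protocol (assumed)**
- f, the share of patients who answer items 2 and 3 by the labels. It is varied over its whole range, 0 to 100%, and taken to be unrelated to the size of a patient's change. Each patient is taken to answer in the same way at baseline and follow-up.
- A 2-point change, for illustration only.

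The protocol states no figure on this point, so there is none to reproduce.

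**Step 1. Weight of the affected items.** 1/3 + 1/3 = 2/3, or 66.7% of the score.

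**Step 2. Mean score change.** Let I be the mean change in intensity and X the mean change in interference.

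Score change = I/3 + (2/3) × [(1 − f) × X + f × I]

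The departure from the intended score change is (2/3) × f × (I − X). It is zero when f = 0, and also when intensity and interference change by the same amount.

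**Step 3. Interference changes by 2, intensity unchanged (X = 2, I = 0).** The intended change is (0 + 2 + 2)/3 = 1.33. The observed change is 1.33 × (1 − f).

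| f | Observed change |
|---|---|
| 0 | 1.33 |
| 25% | 1.00 |
| 50% | 0.67 |
| 100% | 0 |

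**Step 4. Intensity changes by 2, interference unchanged (I = 2, X = 0).** The intended change is (2 + 0 + 0)/3 = 0.67. At f = 100% the observed change is (2 + 2 + 2)/3 = 2.00.

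**Step 5. Effect on the level of one patient's score.** With assumed values of intensity 6 and interference 3, the intended score is (6 + 3 + 3)/3 = 4.0. A patient who answers all three items as intensity scores (6 + 6 + 6)/3 = 6.0. The shift is (2/3) × (6 − 3) = 2.0.

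**The case against.** The strongest reply is that patients read the question before the end labels. The questions in items 2 and 3 are clear, and the form's title names both intensity and interference. If everyone answers the question, f = 0 and nothing is distorted. This stands: misrecording is possible, not shown, and the zero end of the table in the working is an outer bound. It would need every patient to follow the labels while interference improved and intensity stayed still.

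The conflict with section 8.1 is also narrower than it first looks. That section's upper label does not name interference either. The mismatch lies in the zero label and in the word pain in the upper label. At zero, a patient with no pain has no pain interference, so the ambiguity falls mainly on patients who have pain but little interference.

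Answers are collected on the patient's own mobile device, and the live screens are not shown in the protocol. They may carry other labels. That is a reason to check them. It does not dispose of the point, because Appendix 8 presents this form as part of the patient ePRO packet. The label text is complete and identical under all three items, so this is not a gap in the text.

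A reader might go further and infer that the form biases the comparison towards the device. The documents do not support that: both arms complete the same instrument, and nothing indicates that f would differ between them. Equally, the shared form does not restore what the score is said to measure.

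**Conclusion.** The mismatch is confirmed on the face of the protocol: items 2 and 3 of the Appendix 8 form ask about interference and offer an intensity scale, while section 8.1 counts them as interference items with a zero that allows for no interference. They carry 2/3 of the PEG average.

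The size of the consequence is unknown. For an assumed 2-point change in interference alone, the recorded mean change lies between 1.33 and 0, depending on a share f that the documents do not give. The distortion shrinks as intensity and interference move together. A reader might infer that the pain score measures intensity only, or that a loss from 1.33 to 0 is to be expected. Neither follows, since the questions still ask about interference.

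This is a minor construct-validity flaw in one of four primary measures. It does not by itself favour an arm, and it is worth correcting because the correction is cheap and cannot be made at the analysis stage.

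**What to change.** Replace the end labels of PEG items 2 and 3 in Appendix 8 with interference labels that agree with section 8.1. Take the exact wording from the instrument source cited on the form, rather than composing it from section 8.1, whose single description covers all three items. Confirm before enrolment that the deployed ePRO screens carry the same labels.

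If data have already been collected under the printed labels, keep the labels constant within each patient, because a switch between baseline and follow-up would make that patient's scores non-comparable. In that case, also report item 1 separately from items 2 and 3, so that readers can see whether they move differently.

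Before enrolment the cost is two labels on an electronic form and one check of the live screens. After enrolment has begun it is the added item-level reporting and the handling of patients already under the printed labels.

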4.1 Phase II Study Assessment Tables

 Initial Study Assessments Table 												
*Evaluations are completed weekly, every 7 days ± 3 days												
Nu-V3 Treatment Arm Evaluation*	Week 1	Week 2	Week 3	Week 4	Week 5	Week 6	Week 7	Week 8	Week 9	Week 10	Week 11	Week 12
Informed Consent	x											
Inclusion and Exclusion ¹	x											
Patient Registration ¹	x											
Medications Form ¹	x			x				x				x
Patient Onboarding and Orientation ²	x											
In office assessment	x	x	x	x	x	x	x	x	x	x	x	x
New Device Placed ³	x				x				x			
Pad Replaced ³		x	x	x		x	x	x		x	x	x
Treatment Forms ¹	x	x	x	x	x	x	x	x	x	x	x	x
No Device												
HRV Assessment (optional) ⁴	x	x	x	x	x	x	x	x	x	x	x	x
ePRO Questionnaires ⁵	x	x	x	x	x	x	x	x	x	x	x	x
Patients' Global Impression of Change ePRO form (PGIC) ⁵		x	x	x	x	x	x	x	x	x	x	x
Providers' Global Impression of Change ePRO form (PGIC) ¹		x		x		x		x		x		x
Optional Patient Media Testimony ⁶	x	x		x				x				x

1. Inclusion/Exclusion, Registration, Medications, Treatment, and Providers' PGIC forms to be completed by site via online module.
2. Patient Onboarding and Orientation includes introductory demographics form, Nu-V3 patient training video
3. Upon having three consecutive weeks of primary symptom reduction of $\geq 70\%$ via patient reported numerical scales from baseline, the participant will have reached symptom response plateau and will continue as described in the study assessments table, but without device therapy. Then if the participant's primary symptom score increases at any time by $\geq 20\%$ from the symptom response plateau, they may again continue device therapy until week 24.
4. (Optional) HRV assessment will be conducted before the first treatment and again 15-20 minutes following the first treatment. The HRV assessment will also be conducted prior to each weekly treatment. This assessment is applicable to participating sites per the clinical trial agreement. Contact the clinical trial manager for Information.
5. ePRO questionnaires completed on patient's mobile device: DQ-9 (baseline), PTB-7, PEG, GAD-7, PHQ-9, PROMIS 4a, PGIC
6. If patient consents to media testimony, site will collect via study collection process.

Nu-Life Solutions Miniaturized Wearable Medical Technology - NuJ ³	Study Assessments Table											NuJ ³
	*Evaluations are completed weekly, every 7 days ±3 days											

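### The GAD-7 form in Appendix 8 gives its zero category an ambiguous label that differs from the one in section 8.1, adding avoidable noise to a primary instrument

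*Protocol*

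**What the plan says.** Protocol section 8.1 names the GAD-7 as the anxiety instrument and gives its item scoring: "values range from 0 ('Not at all') to 3", the top value being 'Nearly every day'. On the total it says: "Items are summed to determine the instrument's score".

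The patient form in Appendix 8 asks, over the last two weeks, "how often have you been bothered by the following problems". Its four columns are scored 0, 1, 2 and 3. The column scored 0 is headed "Not at all sure"; the other three are headed 'Several days', 'Over half the days' and 'Nearly every day'.

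Anxiety counts towards the main result: "The primary effectiveness endpoint is a statistically significant reduction in one or more of measures of: chronic pain, anxiety, depression, or sleeplessness". The footnotes to the section 4.1 assessment tables give the same ePRO list for the treatment and control arms: "DQ-9 (baseline), PTB-7, PEG, GAD-7, PHQ-9, PROMIS 4a, PGIC".

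**The concern.** The label does not answer the question asked. The stem and the three upper categories concern frequency, while the word 'sure' concerns certainty. Two misreadings are possible:

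- A patient who cannot say whether the symptom was present may take the first column as the 'don't know' option and be scored 0, as symptom-free.
- A patient who is certain that the symptom was absent may hesitate over a label that seems to say the opposite of certain, and may choose the next column or leave the item blank.

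Zero is also the category that improving patients should move into, so the ambiguity sits where a treatment effect would show. The GAD-7 contributes to the primary effectiveness endpoint. Under section 8.2 it also feeds the time to a reduction of at least 30% and the mean percentage change for each instrument. The form is completed on the patient's own device, weekly in the treatment arm and at weeks 1, 4, 8 and 12 in the control arm, and the label applies to all seven items each time.

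**Working it through.** The protocol states no figure to reproduce. The check compares the two texts and then looks at the score range.

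**1. The zero label, place by place**

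| Place | Label for 0 | Fits a 'how often' stem? |
|---|---|---|
| Section 8.1, GAD-7 | Not at all | Yes |
| Appendix 8, GAD-7 form | "Not at all sure" | No |
| Section 8.1, PHQ-9 | Not bothered at all | Yes |
| Appendix 8, PHQ-9 form | Not at all | Yes |

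The PHQ-9 form has nearly the same stem as the GAD-7 form. Of the four entries, only the GAD-7 form's label brings in certainty. It is a clean column heading over seven items coded 0, so it does not look like an artefact of text extraction.

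**2. Score range.** Inputs: seven items, each scored 0 to 3, summed (section 8.1 and the form).

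- Minimum total: 7 × 0 = 0. Maximum total: 7 × 3 = 21.
- A symptom-free patient who ticks the first column throughout scores 7 × 0 = 0, the same as under the section 8.1 label.
- A symptom-free patient who avoids the first column on every item and ticks the second scores 7 × 1 = 7. This is an arithmetic ceiling, not an expected error.
- An unsure patient who ticks the first column scores 0 on that item. If the accurate answer was 'Several days', the total is 1 point too low.

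The first misreading in the concern lowers the score and the second raises it.

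**3. What one point is worth on the percentage endpoints.** The protocol gives no expected baseline mean. Purely as illustration, take the two severity values that section 8.1 mentions, 10 and 15, as baselines:

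- Baseline 10: a 30% reduction is 0.30 × 10 = 3 points, and one item misread by one category is 1/10 = 10 percentage points.
- Baseline 15: a 30% reduction is 0.30 × 15 = 4.5 points, and one item misread by one category is 1/15 = 6.7 percentage points.

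So one misread item is not negligible for the patient concerned. How many patients would misread an item cannot be derived from the protocol.

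**4. Effect of the correction on scoring.** Relabelling the first column leaves the coding unchanged: 0 to 3 per item and 0 to 21 in total.

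**The case against.** The strongest reply is that the form still works. The column carries a printed 0, is the lowest of four ordered categories and is the only one below 'Several days'. The follow-up question, addressed to patients who checked off any problems, also implies that the first column means no problem. This stands. A reader might infer that a symptom-free patient has no valid answer, or that the anxiety endpoint is invalid; the form supports neither.

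Second, section 8.1 words its anchors loosely: its PHQ-9 labels also differ from the PHQ-9 form, so it need not be a verbatim specification. That is fair, but the PHQ-9 variants mean the same thing, whereas the added word on the GAD-7 form changes the meaning.

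Third, a reader might infer that patients are left to interpret the form with no contact at all. Section 4.0 includes staff time for verifying ePRO completion in the treatment sessions, and all four control ePRO weeks coincide with an in-office assessment. This limits skipped items, but only in part: checking completion is not checking interpretation, and treatment-arm weeks 15, 18 and 21 have ePRO without an office visit.

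Fourth, the live screen is not shown. Appendix 8 is laid out as a paper form, and it contains forms DQ-7 and PTB-6 where the section 4.1 tables list DQ-9 and PTB-7. The phone may therefore not carry this label. That is a reason to check the screen; the appendix still needs correcting.

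Finally, the severity values 10 and 15 are only descriptive in section 8.1. Eligibility uses a separate 0 to 10 rating and the null hypothesis concerns mean scores, so no decision rests on a shifted cut-off.

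**Conclusion.** The discrepancy is real and minor. Appendix 8 puts an ambiguous label on the zero category of a patient-completed primary instrument, in conflict with section 8.1 and out of step with the stem of its own form. The consequence is avoidable measurement noise in the GAD-7, of unknown size and direction.

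Two stronger conclusions are tempting. One is a definite error of several points. The 7-point ceiling requires a symptom-free patient to reject the zero column on all seven items, and nothing in the protocol suggests how often even one item would be affected. The other is that the treatment difference would be biased towards zero. Hesitant symptom-free patients score too high and unsure patients score too low, either can happen at baseline or at follow-up, and both arms use the same form. The wording alone therefore gives no reason to expect bias between arms.

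The conclusion assumes that the Appendix 8 form reflects what patients see, which the protocol does not confirm.

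**What to change.** Change the heading of the zero column on the Appendix 8 GAD-7 form to 'Not at all', to match section 8.1. Check the live ePRO screen and correct it if it carries the same label. Do both before first use.

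The cost is one text correction in the appendix and, if needed, one in the ePRO build; scoring and analysis do not change. The only downside arises if data have already been collected, because the change would then mix two wordings within patients. In that case, record the date of the change and identify the visits completed under the present label, so that the analysis can take account of them.
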